Cover page

Official Title of the study: Family-based Mindfulness Training for Promoting Child Development and Stress Management in Economically Disadvantaged Families

NCT number (if available): NCT ID not yet assigned

Date of the document: September 18, 2017

Application of mindfulness training in a family-based intervention for improving development and stress management for children in economically disadvantaged families

Study Objectives

1. To investigate the effectiveness of a FBMI in reducing parental stress and promoting child development
2. To develop an evidence-based practice approach for reducing stress of EDF in Hong Kong Chinese context.
3. To add to theory and develop a better understanding of factors related to EDF and child development to aid policy makers and practitioners working with them

Research plan and methodology

Hypotheses of the study

In responding to the objectives proposed in last section, we hypothesize that the children in the intervention will have lower physiological stress, less behavioral problems, better attention, behavioural and emotional regulation than participants in the control group at the end of intervention, and parents in the intervention will have lower physiological stress and self-reported parental stress, less anxiety and depressive symptoms, better mindfulness in parenting and perceived family functioning than participants in the control group at the end of intervention.

Research plan

The effects of this family-based intervention will be tested using a two-arm randomized controlled trial, comparing the family-based mindfulness intervention (arm 1) to a wait-list control (arm 2). After the completion of the programme and a three month follow-up, participants in arm 2 will be given the same intervention. Assessments will be made before (T1) and after intervention (T2) and at the three month follow-up (T3). Programme effects can be tested using both between-subject (comparison of two arms) and within-subject (comparison of measures at T1, T2, and T3).

Sample size estimation. There are two primary outcomes in this study. Outcomes of two mindfulness training by Bogels and colleagues (2013), with an effect size of 0.4 in parental stress, and the one by Black and Fernando (2010), with an effect size of 0.4 in paying attention and selfcontrol, are chosen for sample size calculation. For a two-tailed α error of 5%, an 80% power, and a test of two independent groups, the required sample size will be 100 families per arm (Cohen, 1988). With references to two local mindfulness training studies which reported 30% drop-out rate (Hou et al., 2013; Lo et al., 2013), we aimed to recruit 130 families per group, and 260 families for two arms in total.

Recruitment of participants. Considering the feasibility of recruiting a large number of economic disadvantaged families and the arrangement of intervention programme within their living district, three districts (Kwai Ching, Kwun Tong, and Sham Shui Po), which ranked the first, third, and the fourth among 18 districts in Hong Kong, in terms of percentage of the children aged 0 to 15 from low income families (Census and Statistical Department, 2013). All kindergartens joining the education voucher scheme which are affordable to low income families in above three districts will be assigned a random number. Kindergartens will be randomly selected, and all K2 and K3

parents from the kindergarten will receive an invitation to participate in this study. Interested participants will be assigned to two arms randomly. The randomization allocation is administered by an independent research assistant who is blind to the identity of participants and will not be involved in contacts with families and programme implementation. With the estimation of an average response rate of 40%, and a 33% of families in these districts are families in economic disadvantaged, 1500 invitations are required to meet the expected sample size. Quota will be divided by three districts according to their number of student populations proportionally. At the beginning of the study, parents of the participating schools will be asked to complete the parenting stress inventory and demographic information. Inclusion criteria of this study include: (1) monthly household income below one half of the median of those in Hong Kong; (2) moderate to high parental stress: to be assessed by a self-reported inventory Parenting Stress Index Short Form (PSI-SF) (Abidin, 1990). A cut-off point of 100 is selected, as reported by Lam as the mean in her sample, and only parents with a PSI score of 101 or above will be included in this study. The only exclusion criteria will be children or parents with disability. Families are formed into groups of 20 to 25 for programme implementation.

Procedures

Programme planning and training. The programmes for parents and children were developed by following the first three steps in intervention research, which was proposed to be completed a large scale of clinical trial was conducted (Feaser & Galinsky, 2010). First, develop programme theories: FMBI adopted themes and approaches about stress responses, with reference to the chronic situation of poverty, and promote the use of acceptance and approach coping in the programmes. Two evidence-based mindfulness training programmes were selected for further adaptation for the present project. The parent mindfulness training is a brief version of the Mindful Parenting course developed by Bogels and Restifo (2014). The evidence-based programme was originally developed for reducing the stress of parents of adolescents with ADHD or aggression (Bogels et al., 2013). The protocol for the child programme was developed by Eline Snel (2013), which was suitable for children at ages from 5 to 8. Concerning the suitability of a programme for coping with poverty-related stress, Wadsworth (2012) highlighted three major principles for promoting effective responses to stress: addressing the involuntary stress responses, appraising the controllability of the situation using approaching-oriented coping, and selecting coping method that matches the specific stressor. Both parent and children programmes follow the mechanisms of mindfulness training, assisting participants to address, acknowledge and accept difficult experiences, and develop self-care strategies or plan for mental health. For children programme, seeking help from adults including parents, caregivers, or other significant others in view of their own limitation of resources (Wadsworth, 2012). This component will be added to the 8 week mindfulness programme for children.

Second, programme structure and processes in the intervention design. In the first draft of the parent programme contents were developed by the principal researcher. Five experienced mindfulness training instructors formed a practice team and gathered for providing comments to the session contents for three times before the pilot studies. Two overseas reviewers were further invited to comment the programme content and responded to the proposed areas of modification for finalizing the intervention protocol. Third, refinement of the protocol in pilot study. Pilot tests have been conducted in 2013/14. Minor modification was made in each of the three major components of a mindfulness-based intervention, namely, in-class mindfulness exercises,

discussion of relevance to context, and home exercises, after the second round of practice team meeting and consultation with overseas reviewers.

Four instructors will be recruited to conduct the programmes. They should have a bachelor degree in social work, psychology, education, or nursing, and complete a basic eight week mindfulness training programme. They are required to complete instructor's training, either a two day training for parent programme, or a six day training for child programme. Please refer to table 1 and table 2 for the sessions outline for programmes for children and parents.

The applicant has conducted two pilot studies to explore the feasibility of FBMI from May to October 2014. Pilot study 1 implemented to six children at 5 and found that they had improved in anxiety-depression symptoms ($t=2.61$, $p=.05$) and attention accuracy ($t=2.63$, $p=.02$). Pilot study 2 was implemented to 10 parents and their children. (to be completed in two weeks).

Implementation and assessment. After the first assessment (T1), the participating families in arm 1 receive eight session mindfulness training. After the intervention, students in both arms will complete the second assessment of the study (T2). Participants in the wait-list (arm 2) will not receive any intervention during this phase. Each session lasts 60 minutes for children and 90 minutes for adults and a 10 minute daily home practice is required. In view of the age factor, a smaller group size of 6 to 8 was adjusted for the children after the pilot study, and a size of 16 to 18 remained for parent group. The class sizes are identical to the recommendation of mindfulness training programme as proposed by overseas training bodies and was confirmed by the overseas reviewers (Kabat-Zinn, 1990; Snel, 2013). Session plans of two programmes are attached in Appendix 1. Three Non-government organizations have committed to participate in the study. They are Hong Kong Family Welfare Society, Christian Family Service Centre, and Yang Memorial Methodist Social Service. Programmes will be conducted in their family service centres at Kwai Chung, Kwun Tong, and Mongkok. Each centre will be responsible for conducting intervention programmes for the families recruited within or in a nearby district. Participants in the wait-list (arm 2) will receive the same intervention after three month follow up (T3).

Intervention fidelity. The intervention will be assessed for fidelity of implementation by videotaping all group sessions. Two independent experts in mindfulness training will be recruited to view six randomly selected clips and rate the level of compliance to the intervention protocol. High concordance rate between two experts signifies great fidelity to intervention.

Additional qualitative studies to offset the threats of internal validity. 1. Parent's weekly diary: The use of weekly diary for recording the use and reflection of homework exercises is a regular practice in MBCT (Segal, Williams & Teasdale, 2013). Weekly diary is also a common evaluation strategy to examine programme effect and it has also been used in local intervention study (Shek, 2010). For each parent group, two parents will be randomly assigned to write up their experiences, feelings and thoughts about stress and their coping in daily life. Since the participants are from economic disadvantaged families, research assistants will confirm with selected participants if they are literate and feel competent to submit their diary. 2. Focus group interviews: All parents will be invited to participate in the 8th week and attend a focus group interview. They will be gathered face-to-face to reflect and share their perception about the programme and the changes their family experience after joining the programme. The procedure of the interview will be structured, addressing topics about participant' overall conditions about their family stress, their reports of changes after joining the intervention programmes, their attributions about changes, and the helpful and unhelpful components of the programmes. The interview protocol is adapted from Client Change Interview (CCI) developed by Elliott, Slatick and Urman (2001).

Measures

Figure 1 list out all variables and measures to be used in this study.

Demographics. Questions about age and gender of parent and child, place of birth, number of family members and children, parent's marital status, household income will be asked.

Child functioning

1. physiological stress. Salivary cortisol and HRV are useful biomarkers that have been selected as outcome measures for mindfulness-based intervention (Matousek, Dobkin & Pruessner, 2010; Nijjar et al., 2014). They are also useful stress indicators for young children (Blair et al., 2011a; Michels et al., 2013).

Salivary cortisol: Salivary cortisol of both parents and children will be collected by Salivette tubes. Two saliva samples (wake up and 2100 h) at two time-points (T1, T2) on two consecutive days are used. The participants were reminded not to brush their teeth or eat within thirty minutes before sample collection to avoid contamination and were advised to follow their normal daily routines otherwise. Collected tubes were kept frozen until they underwent laboratory analysis of the salivary cortisol using an enzyme-linked immunoassay kit (Salimetrics, PA, USA). *Heart Rate Variability (HRV):* HRV is a measure of cardiac autonomic function by counting the cyclic variations of RR intervals in electrocardiogram. It is also an early marker of cardiovascular risk (Taylor, 2010). HRV will be measured by using ambulatory electrocardiogram to reflect on mother's cardiovascular risk and autonomous nervous system functioning. Polar heart-rate monitors (Polar Vantage NV, Polar Electro Oy, Finland) will be used to continuously collect heart-rate data (in the form of R to R peak intervals) from the mothers for 30 mins. During the HRV assessments, the participants will be asked to do a stressful computer game to create an acute stressful environment. The participants' spectral HRV data including (1) normalised low frequency (LF) power (0.04-0.15 Hz), (2) normalised high frequency (HF) power (0.15-0.4 Hz) and (3) the low frequency/high frequency (LF/HF) power ratio will be recorded by using Kubios HRV version 2.1 software package (Biosignal Analysis and Medical Imaging Group, University of Eastern Finland, Finland).

2. behavior problem. The Chinese-Cantonese version of Child Behavior Checklist (CBCL) will be used to assess child behaviour problems through collection of parent's ratings (Achenbach & Rescorla, 2000). The test-retest reliability and criteria validity of the school children version of CBCL have been established for Hong Kong (Leung et al., 2006). However, a preschool version CBCL/1.5-5 which applies to children aged 1.5 to 5 was developed in 2000 forming a similar factor structure in Mainland and overseas studies (Liu, Cheng, Leung, 2011). It has 67 items involving seven subscales (emotionally reactive, anxious/depressed, somatic complaints, withdrawn, aggressive behavior, attention problem, sleep problems). The first four was classified as internalizing problems and the following two was classified as externalizing problems, and such factor structure were confirmed in Mainland's study. Correlations between seven subscales ranged from 0.38 to 0.71 and those between internalizing and externalizing problems was 0.75 (Liu, Cheng & Leung, 2010).

3. attention. The Child Attention Network Test (ANT) was developed by Posner and Petersen (1990). It presents five fish in a horizontal row that appear above or below the fixation point. Children were instructed to press a key indicating in which direction the central fish was pointing

and to ignore the flanker fishes. Completion of the task allows calculation of three scores related to the efficiency of attention networks. Alerting is measured by the additional time required to respond with no cue, compared to a cue that inform the child that a target will occur shortly. Orienting is measured by the time taken to respond to a cue at the target location minus reaction time to a central cue. Executive attention is measured as interference by the flanker fish on the child's score. The ANT was used in one of the Co-Investigator's pilot study for mindfulness training for ADHD children (Wong, Kwok & Lam, 2012).

4. emotion and behaviour regulation. A two dimensional assessment will be used and scores from both tests will be combined to form the child's assessment of emotion and behaviour regulation. The Snack Delay and the Toy Wrap tests are used to assess the child's emotional and behavioral regulation. In the Snack Delay test, children are instructed to put their hands flat on the table and watch a snack being placed under a cup. They can wait until the assessor tells them that "time is up" that they can have the snack. The assessor administers four trials, which last 10, 20, 30, and 60 seconds respectively. The assessor scores each trial using a four point rating (1=eats snack, 2=touches snack, 3=touches cup or timer, 4=waits for time and does not touch cup or timer). The mean score across four trials will be the score of child's emotional and behavioral regulation. In the Toy Wrap test children are asked not to peek while assessor wraps a toy in tissue and bag for one minute. The latency in seconds to first touch of toy will be measured. In the selection of test, a rule of not having more than 50 percent of participants got highest scores will be observed (Bassett, Denham, Wyatt, & Warren-Khot, 2012). Construct validity of this measure was evaluated in the applicant's pilot study in 2014. In a study with 8 samples, the Snack Delay was significantly negatively correlated with emotionally reactive syndromes ($r = -.82, p < .05$), aggressive behaviors syndromes ($r = -.79, p < .05$), externalizing problems ($r = -.80, p < .05$) and total problems ($r = -.73, p < .05$) in parent-reported Child Behavior Checklist. In a study with 7 samples, the Toy Wrap was significantly negatively correlated with attention problems ($r = -.80, p < .05$), internalizing problems ($r = -.86, p < .05$), externalizing problem ($r = -.77, p < .05$) and total problems ($r = -.84, p < .05$).

5. cognitive and language development. The Hong Kong Early Child Development Scale has been developed for assessing the children from three to six for their overall development conditions (Rao et al., 2013). Within the eight domains, language development (13 items), pre-academic learning (27 items), and cognitive development (10 items) will be selected for the present study. Cronbach's alphas of the above three subscales are .80, .95, and .70 respectively. Normative data for K3 students in Hong Kong is available for comparison (Rao et al., 2013).

Parent functioning

1. physiological stress. Salivary cortisol and HRV of parents and data collection follows same procedure as child salivary cortisol and HRV.

2. parental stress Parenting Stress Index Short Form (PSI-SF) The Parenting Stress Index Short Form has 36 items and was developed by Abidin (1990) for tapping the sources of difficulties and level of parenting stress experienced by parents. The scale was divided into three subscales,

parental distress, parental-child dysfunctional interaction, and difficult child. The Chinese version was validated by Lam (1999). The reliability estimates for the total score and three subscales were 0.92, 0.86, 0.82, and 0.86 respectively.

3. mental health. Anxiety and depression symptoms are assessed by The Chinese-Cantonese version of Hospital Anxiety and Depression Scale (HADS), originally developed by Zigmond and Snaith (1983). It consists of two sub-scales with seven items related to the level of depression and anxiety respectively (Leung et al., 1993). The Chinese-Cantonese version of HADS shows good convergent validity with close correlation with both the Hamilton rating Scale of Depression (HRSD) and the Hamilton Rating Scale of Anxiety (HRSA) (Leung et al., 1999). The Cronbach's alpha coefficients are .80 and .71 for the anxiety and depression subscales respectively and its split-half r is 0.86.

4. interpersonal mindfulness. The Interpersonal Mindfulness in Parenting (IM-P) has 31 items that assess the parent's quality of mindfulness in specific to their family context (Duncan, Coatsworth, & Greenberg, 2009). The original subscales include listening with full attention, emotional awareness of self and child, self-regulation in parenting relationship, non-judgmental acceptance of self and child, and compassion for self and child. The inter-item coefficient ranged from 0.45 to 0.72. IM-P was found to mediate the effects of family-based mindfulness intervention (Coatsworth et al., 2010). A validation study of IM-P on Hong Kong parents with preschool children will be conducted by the P-I on late 2013.

Analysis

Quantitative data: Baseline equivalence. The values of the primary outcome measures (i.e., parental stress and child behavior problem) at T1 will be compared among participants in the two trial arms. The outcomes at T1 and the treatment-condition variable will be used as the dependent variables, after controlling for age and sex of child.

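### On the plan's own rates, 1500 invitations yield about 198 families rather than the 260 to be recruited, and the parenting-stress entry criterion is not counted at all

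*Combined protocol and SAP*

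**What the plan says.** *Sample size estimation* takes an effect size of 0.4, a two-sided 5% error and 80% power, and concludes that "the required sample size will be 100 families per arm". It then allows for 30% drop-out and sets a recruitment aim of 130 per group, or "260 families for two arms in total".

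*Recruitment of participants* gives the sampling frame: "All kindergartens joining the education voucher scheme which are affordable to low income families in above three districts will be assigned a random number". Kindergartens are then drawn at random, and all K2 and K3 parents in those drawn are invited. The invitation count rests on two rates, introduced by "With the estimation of an average response rate of 40%, and a 33% of families in these districts", and ends with the statement that "1500 invitations are required to meet the expected sample size". The plan does not say which sample size is meant. On the districts it adds: "Quota will be divided by three districts according to their number of student populations proportionally".

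Entry has a second condition besides low income. On the PSI-SF, "A cut-off point of 100 is selected", this being the mean of an earlier sample, and "only parents with a PSI score of 101 or above will be included in this study". Families in which the parent or child has a disability are excluded. No rate is given for the PSI-SF condition or for the exclusion.

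**The concern.** An invitation count has to deliver the number of families to be randomised. Here the two stated rates multiply out to about 200, which is the total needed before the drop-out allowance and not the 260 that the plan sets out to recruit. It appears that the allowance was never carried into the count.

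The calculation also stops after response and income, although a parent must pass the PSI-SF threshold to enter. Since that threshold was the mean of an earlier sample, the loss could be substantial.

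A team that schedules kindergarten draws and screening on 1500 invitations would under-plan both by about a quarter, before any PSI-SF loss. If recruitment actually stopped at 1500, the trial would start without the margin it added for drop-out.

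**Working it through.** **Inputs from the documents.** Invitations 1500, response 0.40, disadvantaged share 0.33 (*Recruitment of participants*). Required 100 per arm, recruitment aim 130 per arm and 260 in total, drop-out 30%, effect size 0.4, two-sided 5%, power 80% (*Sample size estimation*).

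**1. The plan's own figures.**
- A two-sided two-sample t-test at effect size 0.4 and 80% power needs 99.1 per arm, so the stated 100 reproduces.
- Invitations = target ÷ (response × share). For 200 families: 200 ÷ (0.40 × 0.33) = 1,515, and with one third 200 ÷ (0.40 ÷ 3) = 1,500 exactly.
- For 260 families: 260 ÷ (0.40 × 0.33) = 1,970, and with one third 260 ÷ (0.40 ÷ 3) = 1,950.

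So 1500 reproduces from 200 and does not reproduce from 260.

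**2. Yield of 1500 invitations.**
- 1500 × 0.40 × 0.33 = 198, which is 62 short; 198 ÷ 260 = 76%.
- With one third: 1500 × 0.40 ÷ 3 = 200; 200 ÷ 260 = 77%.

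**3. Adding the PSI-SF criterion.** The documents give no pass rate, so 80% and 50% are assumptions. The only anchor is that the cut-off was the mean of an earlier sample. About 50% is plausible only if those scores were roughly symmetric and the two populations are similar. Rows use the 0.33 share; responders are 40% of the invitations in the third column.

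| Assumed pass rate | Families from 1500 | Invitations for 260 | Responders to screen |
|---|---|---|---|
| 100% | 198 | 1,970 | 788 |
| 80% | 198 × 0.8 = 158 | 1,969.7 ÷ 0.8 → 2,463 | 985 |
| 50% | 198 × 0.5 = 99 | 1,969.7 ÷ 0.5 → 3,940 | 1,576 |

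With one third, the last two invitation counts are 1,950 ÷ 0.8 ≈ 2,438 and 1,950 ÷ 0.5 = 3,900. The plan's 1500 implies 1500 × 0.40 = 600 responders.

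**4. Share that would rescue 1500.** With 600 responders, reaching 260 needs a disadvantaged share of:
- 260 ÷ 600 = 43.3% with no PSI-SF loss;
- 260 ÷ (600 × 0.8) = 54.2% at 80% pass;
- 260 ÷ (600 × 0.5) = 86.7% at 50% pass.

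**5. Power if recruitment stopped at 1500.** Two-sided t-test, effect size 0.4, no clustering, no PSI-SF loss.

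| Basis | 198 enrolled | 260 enrolled |
|---|---|---|
| All randomised analysed, effect undiluted | 99 per arm: 0.800 | 130 per arm: 0.895 |
| Completers after 30% drop-out | 99 × 0.7 ≈ 69 per arm: 0.645 | 130 × 0.7 = 91 per arm: 0.765 |

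**The case against.** The strongest defence is that the sample size in the invitation sentence is undefined and may mean the 200 families required for analysis. On that reading 1500 is exactly right with one third, and *Project funding* does budget completion coupons for 200 families. This explains where the number came from but does not rescue it. Families drop out after they enter, so 260 must be enrolled to leave an allowance. The cortisol line in the same budget, for 520 participants, fits 260 parent-child pairs.

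Second, the 33% describes the districts, while invitations go only through voucher-scheme kindergartens affordable to poorer families. The share among responders could be higher, and 43.3% would close the gap if nobody failed the PSI-SF screen. That stands as a limit on certainty about the real shortfall. The plan states no higher share, however, and draws its own conclusion from 33%.

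Third, nothing caps invitations at 1500, and further kindergartens can be drawn from the numbered list. This also stands, and it confines the main harm to workload and time.

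Fourth, the analysis is by intention to treat with the last observation carried forward, so the completers figures are not on the plan's own basis. On the plan's basis, 198 families nominally keep about 80% power, but only if families who drop out do not dilute the effect. The completers comparison should be read like for like: 65% against 77%, not against 80%.

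Finally, the PSI-SF counts are illustrations. That the criterion is omitted is certain, but the size of the loss is not.

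**Conclusion.** The concern holds: the invitation figure is wrong as written. On the stated rates, 1500 invitations yield 198 to 200 families, 76% to 77% of the 260 to be recruited, before any loss to the PSI-SF criterion or the disability exclusion. This assumes one invitation per family, that the two rates multiply, and that the district-wide 33% holds among responders.

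Confidence is high on the arithmetic and on the omission of the PSI-SF criterion. It is low on the size of the PSI-SF loss and on the true share among responders, because the documents give neither. This should be fixed, but it is recoverable: the target, the randomisation and the analysis are unaffected, and power suffers only if recruitment stops at 1500.

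**What to change.** In *Recruitment of participants*:

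1. Replace 1500 with about 1,970 invitations (1,950 if one third is meant), labelled as the number before the PSI-SF screen.
2. Give the number after the screen over a stated, assumed pass rate, for example about 2,463 at 80% and 3,940 at 50%, and say whether any loss to the disability exclusion is included.
3. State that the sample size meant is the 260 families to be randomised.
4. State that further kindergartens are drawn in random-number order until 260 eligible families have been randomised, and whether the district quota counts invitations or randomised families.

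If 1500 is kept, restate expected enrolment as about 198 before the PSI-SF screen. Restate power as nominally about 80% under intention to treat with no dilution (89% for 260), or about 65% for completers at 30% drop-out (77% for 260).

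The target of 260 and the two arms do not change. The cost is more invitations and more screening: about 788 responders rather than 600 before the PSI-SF adjustment, about 985 at an 80% pass rate and about 1,576 at 50%. Check this load against the research assistant line in *Project funding*.

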| 6 | Communicate with mindfulness | 
 • communicate needs and wants in parenting and family relationship |
| 7 | Self-care of parents | 
 • promote self-care for supporting children and family in adversity • consolidate learning |
| 8 | focus group interview | 
 • embedded for research purpose • investigate the mechanism of change |

Figure 1

Variables and measures of the proposed study

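### As most naturally read, arm 1 parents attend a focus group on perceived change before the T2 questionnaires, while arm 2 has no counterpart; the plan should put T2 first

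*Combined protocol and SAP*

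**What the plan says.** **Focus group.** Under Additional qualitative studies, the plan states "All parents will be invited to participate in the 8th week and attend a focus group interview". Of the parents it says "They will be gathered face-to-face to reflect and share their perception about the programme and the changes their family experience". The structured topics are the family's overall stress and then "their reports of changes after joining the intervention programmes, their attributions about changes, and the helpful and unhelpful components of the programmes".

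**Place in the programme.** The parent table in Appendix 1 has eight rows. Row 8 is the focus group interview, whose first listed goal is "embedded for research purpose". That row lists no training content.

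**Timing of T2.** Implementation and assessment says that "the participating families in arm 1 receive eight session mindfulness training" and then "After the intervention, students in both arms will complete the second assessment of the study (T2". The Research plan gives the general schedule: "Assessments will be made before (T1) and after intervention (T2) and at the three month follow-up (T3".

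**Arm 2.** The wait-list arm has no intervention in this phase and is offered the programme after T3 (Implementation and assessment).

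**Outcomes and model.** The PSI-SF is a self-report, the CBCL is rated by the parent, and HADS and IM-P are also parent questionnaires. The between-arm model takes the T2 outcome as dependent variable and adjusts for T1 (Analysis, Intervention effects).

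**The concern.** Parents in one arm are asked to say, in front of other participants, how their family has changed since joining and why. If they then rate parenting stress and their child's behaviour, the ratings may be pulled towards what they have just said or heard. Parents in the other arm rate the same scales without that experience.

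The comparator is a wait-list, so parents know their arm, and these outcomes are their own reports. Some reporting bias is unavoidable in such a design. A component due to the order of procedures is avoidable. It would arise after T1 and in one arm only, so in the T2 comparison it is inseparable from the treatment effect. It would also enter arm 1's T1-to-T2 change, which the within-subject analysis reads as a programme effect. The qualitative work is offered as protection against threats to internal validity, and this timing could add one.

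**Working it through.** **1. Order of events**

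| Step | Arm 1 parents | Arm 2 parents | Source |
|---|---|---|---|
| T1 | assessed | assessed | Research plan |
| Sessions 1 to 7 | programme | nothing | Appendix 1; Implementation and assessment |
| Session 8, week 8 | focus group | nothing | Appendix 1; Additional qualitative studies |
| T2 | assessed after the intervention | assessed | Research plan; Implementation and assessment |
| T3 | assessed at three months | assessed | Research plan |
| After T3 | none planned | programme | Implementation and assessment |

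If the intervention is the eight sessions, T2 follows the focus group. The invitation to all parents is not limited to arm 1 in words, but the topics presuppose having joined the programme, and by week 8 only arm 1 has done so. No section puts the T2 questionnaires before session 8, sets a gap after it, or gives arm 2 a parallel interview.

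**2. Which outcomes are exposed**

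- PSI-SF: parental stress is a primary outcome in both Sample size estimation and Analysis (Baseline equivalence).
- CBCL: child behaviour problems are primary in Analysis. Sample size estimation instead bases its second calculation on attention and self-control.
- HADS and IM-P: parent questionnaires, exposed but not named as primary.
- Cortisol, HRV, the attention test and the child regulation tasks: less open to this effect.

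**3. The plan's own figure**

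Inputs from Sample size estimation: two-sided alpha 5%, power 80%, effect size d = 0.4.

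n per arm = 2(1.96 + 0.8416)² / 0.4² = 2 × 7.849 / 0.16 = 98.1, which rounds up to 99. The t-test version gives 99.1, rounded up to 100. The stated 100 per arm is reproduced.

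**4. Sensitivity to an assumed shift**

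The documents give no size, so b is an assumption: the average reporting shift in arm 1, in SD units. With n = 100 per arm, se = √(2/100) = 0.1414.

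If there is no true effect, P(reject) = Φ(b/se − 1.96) + Φ(−b/se − 1.96). Example for b = 0.10: b/se = 0.707, so Φ(−1.253) + Φ(−2.667) = 0.1051 + 0.0038 = 10.9%.

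If the true effect is 0.4 and the shift goes against the programme, the expected difference is 0.4 − b and power falls.

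| Assumed b (SD) | Share of planned 0.4 | Type I error, no true effect | Power if the shift is unfavourable |
|---|---|---|---|
| 0 | 0% | 5.0% | 80.7% |
| 0.05 | 12.5% | 6.4% | 69.7% |
| 0.10 | 25% | 10.9% | 56.4% |
| 0.15 | 37.5% | 18.6% | 42.4% |

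At the recruitment target of 130 per arm, type I error for 0.05, 0.10 and 0.15 SD is 6.9%, 12.7% and 22.7%. More families do not help, because the shift does not shrink with n. These figures use the plan's simple two-group comparison and ignore clustering and the gain from adjusting for T1. They show sensitivity and do not estimate the bias.

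**5. Session count**

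Implementation and assessment counts eight sessions of mindfulness training for arm 1 families. Appendix 1 gives parents 8 − 1 = 7 programme sessions plus a research interview. This is a separate inconsistency and says nothing about the size of any bias.

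**The case against.** A reader might infer that the documents fix the order and put the focus group immediately before T2. They do not. If session 8 is research and not training, the intervention could be taken to end at session 7, with T2 before or at the week-8 visit. Appendix 1 lists baseline collection within parent session 1, so T2 could likewise be collected at session 8. The sentence on T2 names only students, and the parents' timing comes from the general schedule. No interval is given. All this stands. It turns certainty into a natural reading, but under none of the readings is the order protected: even if T2 is collected at session 8, the sequence within that visit is open.

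A reader might also infer that any bias must favour the programme. The topics include family stress and unhelpful components, which could raise reported stress. A favourable shift is likely, because parents are asked about change since joining and its causes, but it is not certain.

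Thirdly, arm 1 parents already know their allocation and have met weekly with discussion, so most reporting bias may come from the design itself. Attendance is by invitation, which would dilute an average shift. The documents do not allow the focus group's own contribution to be separated out. This too stands, and it limits the claim to an avoidable risk of unknown size.

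Finally, only parental stress is certain to be an exposed primary outcome, because the two sections that name the primary outcomes differ on the second.

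**Conclusion.** The point holds as a risk created by the schedule. Read naturally, the plan gives arm 1 parents alone a group discussion of change before unblinded, parent-reported outcomes at the main comparison time, and no section prevents this. That parents are unblinded is inferred from the wait-list design; it is not stated. Adjustment for T1 cannot remove a shift that arises later and in one arm.

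The documents support no estimate of its size. The range of 0.05 to 0.15 SD is an assumption, and zero or a shift in the other direction is possible. It would be wrong to conclude that 12.5% to 37.5% of any observed effect is artefact, or that the T2 comparison is invalid. The case for acting is that the exposure is one-sided, touches a primary outcome and is cheap to avoid. The sample size is unaffected.

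**What to change.** Add a rule to Implementation and assessment and repeat it under Focus group interviews: parents in both arms complete all T2 questionnaires (PSI-SF, CBCL, HADS, IM-P), at matched calendar times, before any focus group is held. This can be done at or before the week-8 visit, or by moving the focus group after T2. State the interval between the last programme session and T2, and say that parents as well as children are assessed then.

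The cost is small but not nil. By the plan's own item counts the four questionnaires total 36 + 67 + 14 + 31 = 148 items, and the plan itself raises parents' literacy when describing the diaries. Completing them at the start of week 8 lengthens that visit; holding the focus group after T2 makes it later and may need another gathering. No measure, sample size or analysis changes.

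Separately, reconcile the eight training sessions in Implementation and assessment with the parent table in Appendix 1, and describe session 8 the same way in both places.
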